4.1.6 Definition of Baseline

Age, height, weight and Body Mass Index (BMI) recorded at Visit 1 will be presented as baseline characteristics.

For 12-lead ECG, vital signs, physical examination and haematology, clinical chemistry and renal function parameters, baseline values are those recorded at Screening (Visit 1). If no assessment has been conducted at that visit, the last available value before IMP first dose (collected during unscheduled visits before IMP first dose) will be considered as baseline.

For sputum analysis, **CCI** and spirometry baseline values are those recorded at Visit 2 before IMP first dose. If no assessment has been conducted at that visit, the last available value before IMP first dose (collected at the Screening visit or unscheduled visits before IMP first dose) will be considered as baseline.

4.1.7 Definition of Exposure Time and Follow-up Time

All the efficacy analyses are focused on the endpoints collected during the treatment period. For these analyses, the exposure time will not include the time from end of treatment to the follow-up call.

The exposure time in days will be calculated using the following formula:

CONFIDENTIAL

Sponsor:	Zambon S.p.A.	Protocol Number:	Z7224L02
----------	---------------	------------------	----------

- Exposure time (days) = [date of treatment completion/discontinuation - date of first IMP dose + 1].

The exposure time in years will be calculated using the following formula:

- Exposure time (years) = Exposure time (days) / 365.25.

Date of treatment completion will be the date of End of Treatment Visit.

Date of treatment discontinuation will be the date of End of Study Visit for subjects who discontinued the study before the End of Treatment Visit. In case a subject is lost to follow-up, the date of treatment discontinuation will be the date of last Study Visit.

Date of last exposure will not include any visits/calls after the end of treatment.

The follow-up time in days will be calculated using the following formula:

- Follow-up time (days) = [date of study completion/discontinuation - date of first IMP dose + 1].

The follow-up time in years will be calculated using the following formula:

- Follow-up time (years) = Follow-up time (days) / 365.25.

4.1.8 Visit dates

For each visit, the date recorded by the Investigator in the eCRF (variable SVSTDTC in the SDTM SV domain) will be considered as the visit date in all the algorithms and the listings.

4.1.9 Date of First/Last IMP Dose

The date of first IMP dose is the earliest date of IMP dose considering both the eCRF and the recordings from the **CCI** logging system.

The date of last IMP dose is derived as follows. Where **CCI** data is available for the subject, the date of last IMP dose will be defined as the latest date from the **CCI** logging system, with the following exception. Due to the Covid-19 pandemic, for some subjects, Visit 7 was split into a remote phone call (at the scheduled time of treatment completion), followed by an in-clinic visit (for the purpose of collecting pre-dose and post-dose spirometry data to test for bronchospasm). In such cases, the scheduled study treatment period was completed at the time of the remote Visit 7 phone call, but an additional IMP dose was given at the time of the in-clinic Visit 7. In these circumstances, the latest date from the **CCI** logging system will be compared to the penultimate date from the **CCI** logging system and, if the latest date is more than 14 days after the penultimate date (latest date – penultimate date >14), the **CCI** logging system data will be used taking into consideration the penultimate IMP dose as the date of last IMP dose. The date of last IMP dose will be defined as the date of last IMP administration as entered on the End of Study eCRF form only when **CCI** data is unavailable.

Any inconsistency between eCRF and **CCI** logging system data will be discussed before the database lock.

4.1.10 Data Re-Allocation

Data collected at the early termination visit (when used) for discontinued subjects will not be re-allocated. Early termination data will not be moved in the database, however, statistical

CONFIDENTIAL

Sponsor:	Zambon S.p.A.	Protocol Number:	Z7224L02
----------	---------------	------------------	----------

programming will allocate this visit as Visit 7 within the Analysis Data Model (ADaM) datasets.

Potential issues of the approach defined above and other decisions regarding data re-allocation will be evaluated during the blind review of the data and documented in the Blind Data Review and Analysis Sets Report.

4.1.11 Exclusion of Data from the Statistical Analysis

If a subject received the incorrect treatment after being treated with the correct one, all the data collected after the date of the wrong treatment dispensing will be reported in listings and flagged, but not included in the statistical analysis on the ITT, mITT, Safety and PP populations.

Unless stated otherwise, primary efficacy endpoint and related assessments conducted at an early termination visit or unscheduled visit will be included in the statistical analysis, Where not stated differently, other assessments conducted at an early termination visit and unscheduled assessments will not be considered in the statistical analysis, but will be listed only.

Only NCFB pulmonary exacerbations with a start date \geq date of first IMP dose and \leq date of treatment completion/discontinuation will be considered in the analysis.

In case of data excluded from the statistical analysis (in the situations described above but also in other cases, for example: spirometry tests excluded due to technical issues, or assessment not done), the derived variables based on these data will not be calculated. For example, the change from baseline to Visit 5 will not be calculated if the measurement at Visit 5 is excluded from the statistical analysis, or all the changes from baseline will not be calculated if the measurements pre-dose are excluded.

4.1.12 Listings

All data collected will be presented in the listings.

4.2 Interim Analysis

No interim analysis is planned for this study. The trial terminated early, see Section 3.9.

4.2.1 Data [CCI]

Due to the impact of Covid-19 during the conduct of the study, the Sponsor has established a [CCI] Committee [CCI] to evaluate the impact of decisions made [CCI] on the integrity of the study data. Although the [CCI] will only review blinded data, the [CCI] will advise if additional [CCI] analyses may be needed as a result of this pandemic. In addition, the [CCI] will review blinded pulmonary exacerbation data to determine whether or not events have been correctly assigned as meeting protocol-defined criteria. The [CCI] may recommend that sites reconsider their classification of pulmonary exacerbations as meeting the protocol-defined criteria or not (as well as re-examine the duration of the event based on the existing eCRF data), however, the ultimate decision will remain that of the Principal Investigator at each site.

CONFIDENTIAL

Sponsor:	Zambon S.p.A.	Protocol Number:	Z7224L02
----------	---------------	------------------	----------

4.3 Disposition of Subjects

The number of subjects screened and the number of screen failures will be presented (overall). All screened subjects will be included. Re-screened subjects will be counted twice in the number of screened subjects. The number of re-screened subjects will be presented.

The number and percentage of randomised subjects who completed the study, withdrew from the study after randomisation and the number and percentage of subjects with each reason for withdrawal from the study will be presented by treatment group for the ITT population. Summaries of enrolled subjects will be reported overall and by country. These will include a presentation of country, number of subjects randomised and number of subjects who completed the study for the ITT population.

The number and percentage of subjects at Visit 2, who attended Visits 3, 4, 5, 6 and 7 and who had a follow-up call will be presented by treatment group and overall for the mITT Population. Time to completion/discontinuation from the study (days) will be summarised by descriptive statistics and calculated as (date of completion/discontinuation – date of first IMP dose).

The number and percentage of screened subjects who had any inclusion/exclusion criteria deviation as detailed in the eCRF will be reported. Results will be presented also for each criterion.

Protocol deviations affecting the efficacy analyses and protocol deviations specifically related to the COVID-19 pandemic will also be summarised for the Enrolled Population. The number and percentage of subjects included in each analysis population will be presented overall and by treatment group.

4.4 Baseline and Demographic Characteristics

No formal comparison between treatment groups on baseline and demographic characteristics will be done. Unless specifically stated in the relevant section, analysis will be done on the mITT Population.

4.4.1 Demography Characteristics

Demographics will be summarised by treatment group and overall. This will include age, ethnicity, gender, race, employment status, height (cm), weight (kg), BMI (kg/m²).

Summaries will be produced using the mITT and the Safety Population.

Note:

- Age, height, weight, BMI and employment status recorded at Visit 1 will be presented.

4.4.2 Smoking and Alcohol Status

Smoking status at Screening (non-smoker, former smoker or current smoker), will be presented by treatment group and overall for the mITT Population. Former smoker will be further characterised summarising time from last cigarette (years) and number of pack-years.

Alcohol Status (Alcohol consumer: Yes or No) at Screening will be presented by treatment group and overall, along with summaries of alcohol units per week for alcohol consumers.

CONFIDENTIAL

Sponsor:	Zambon S.p.A.	Protocol Number:	Z7224L02
----------	---------------	------------------	----------

Notes:

- For former smokers, time from last cigarette (years) will be calculated as (screening date – date of last cigarette)/365.25;
- In order to calculate the time from last cigarette, the following rules will be applied for partial dates of the last date of smoking:
 - if only the day is missing, the first day of the month will be assumed;
 - if the day and the month are missing, then the first day of the year will be assumed.

4.4.3 Non-CF Bronchiectasis History

The following variables will be summarised for the mITT Population by treatment group and overall:

- Time since diagnosis of non-CF bronchiectasis (years);
- Diagnostic technique used (computerised tomography [CT] or high resolution CT: Yes or No);
- Number of lobes affected (1, 2, 3, more than 3);
- Underlying cause of the bronchiectasis;
- Number of NCFB pulmonary exacerbations requiring oral antibiotics in the last 12 months before Screening;
- Number of NCFB pulmonary exacerbations requiring intravenous antibiotics in the last 12 months before Screening;
- Previous usage of colistimethate sodium/colistin;
- Having at least 1 positive sputum culture for *P. aeruginosa* before Screening.

Notes:

- Time since diagnosis of NCFB (years) will be calculated as (date of Visit 1 – date of diagnosis of NCFB)/365.25;
- In order to calculate the time since diagnosis of NCFB, the following rules will be applied for partial dates of the date of diagnosis of NCFB:
 - if only the day is missing, the first day of the month will be assumed;
 - if the day and the month are missing, then the first day of the year will be assumed.

4.4.4 Past or Concomitant Relevant Diseases, Diagnoses or Surgeries

Past or concomitant relevant diseases, diagnosis or surgeries will be summarised by system organ class (SOC) and preferred term (PT), by treatment group and overall using the mITT Population.

Notes:

CONFIDENTIAL

Sponsor:	Zambon S.p.A.	Protocol Number:	Z7224L02
----------	---------------	------------------	----------

- Past or concomitant relevant Diseases, Diagnoses or Surgeries will be coded according to the Medical Dictionary for Regulatory Activities (MedDRA) version 19.1 or higher;
- Past relevant Diseases, Diagnoses or Surgeries are defined as records in the Medical History eCRF form which are not ongoing at Visit 1;
- Concomitant relevant Diseases, Diagnoses or Surgeries are defined as records in the Medical History eCRF form which are ongoing at Visit 1;
- Terms will be displayed in descending overall frequency (and then alphabetically) of SOC_s and in descending overall frequency (and then alphabetically) of PT_s within each SOC.

4.4.5 Spirometry at Visit 1 and Pre-Dose at Visit 2

The following spirometry parameters will be summarised by treatment group and overall:

- FEV₁ (L);
- Predicted FEV₁ (%);
- FVC (L);
- Predicted FVC (%).

Spirometry results assessed at Visit 1 and at Visit 2 Pre-dose will be summarised using summary statistics for continuous variables. Summaries will be provided for the mITT and for the Safety Population. Results for the Safety Population will be presented along with summaries for spirometry parameters assessed during Visits 3 – 7, inclusive.

More details of the analysis are reported in Section 4.8.2.

4.4.6 Haematology, Clinical Chemistry and Renal Function Parameters at Visit 1

Haematology, clinical chemistry and renal function parameters assessed at Visit 1 will be listed.

More details of the analysis are reported in Section 4.8.4.

4.4.7 Vital Signs at Visit 1

Respiratory rate (breaths per minute), heart rate (beats per minute), systolic and diastolic blood pressure (mmHg) and body temperature (°C) assessed at Visit 1 will be listed.

More details of the analysis are reported in Section 4.8.5

4.4.8 Physical Examination at Visit 1

Physical Examination findings collected at Visit 1 will be listed.

More details of the analysis are reported in Section 4.8.6.

4.4.9 12-Lead ECG at Visit 1

The 12-lead ECG overall interpretation at Visit 1 will be listed.

More details of the analysis are reported in Section 4.8.7.

CONFIDENTIAL

Sponsor:	Zambon S.p.A.	Protocol Number:	Z7224L02
----------	---------------	------------------	----------

4.4.10 Pregnancy Test

Results from the dipstick urine pregnancy test for women of child-bearing potential will be listed only.

4.4.11 Presence of CCI [REDACTED] at Visit 1

Number and percentage of subjects with presence of CCI [REDACTED] collected at Visit 1 will be reported for the mITT Population. Subjects with results CCI [REDACTED] will be considered as negative based on the central lab specifications. The local laboratory result will just record presence or absence of CCI [REDACTED] for eligibility purposes only. The number and percentage of subjects with presence of CCI [REDACTED] as collected in the eCRF will be presented.

4.4.12 CCI [REDACTED] and CCI [REDACTED] B

The CCI [REDACTED] total score and domain scores and the CCI [REDACTED] domain scores at Visit 2 (see Sections 4.7.6.2 and 4.7.6.9 for further details regarding the calculation of the CCI [REDACTED] and CCI [REDACTED]) will be summarised by treatment group and overall using the mITT Population and the PP Population for CCI [REDACTED] and the mITT Population only for CCI [REDACTED] (see Section 4.7.5). Results will be presented along with summaries for results at Visits 3 – 7, inclusive.

4.5 Exposure

4.5.1 Number and Duration of Inhaled Doses

An inhaled dose is defined as any complete or partial dose of IMP that the subject inhaled either at the investigational site or at home (excluding doses $\leq 12.5\%$ as recorded in the CCI [REDACTED] logging system and any final dose recorded in the CCI [REDACTED] logging system that is more than 14 days after the penultimate dose in the CCI [REDACTED] logging system where Visit 7 was split due to Covid-19, as described in Section **Error! Reference source not found.**).

For doses administered at the investigational site, inhaled doses are all doses with a date of administration filled in the “IMP administration under clinical supervision” eCRF page. Complete doses are those recorded as complete in the eCRF. Partial doses are those recorded as non-complete in the eCRF.

For doses administered at home, inhaled doses are all doses with a date and time of administration recorded in the CCI [REDACTED] logging system and dose different than “Null” or “ $\leq 12.5\%$ ”.

The overall number of inhaled doses either at the investigational site or at home will be summarised along with their duration. For doses administered at the investigational site only, the number of complete and partial doses will also be reported.

Summaries will be presented for the Safety and mITT Populations.

Notes:

- All the doses will be recorded in the CCI [REDACTED] logging system, regardless of being administered at the investigational site or at home. Doses administered at home are those not recorded in the eCRF. In case of any inconsistencies between eCRF and CCI [REDACTED]

CONFIDENTIAL

Sponsor:	Zambon S.p.A.	Protocol Number:	Z7224L02
----------	---------------	------------------	----------

data, the **CCI** data will be used in the analysis. While missing date/time of doses might be present in the eCRF, **CCI** data are expected to be complete.

4.5.2 Exposure Days

An Exposure Day (ED) is defined as any day that the subject inhaled at least one full or partial dose of IMP as defined in Section **Error! Reference source not found.**, either at the investigational site or at home regardless of the number of doses on that day. The number of EDs per subject will be summarised overall and by treatment group for the Safety and mITT Populations using descriptive statistics for continuous variables.

4.5.3 Extent of Exposure

Extent of exposure (days) will be calculated using the following formula:

- Extent of exposure (days) = Date of last full or partial inhaled dose of IMP - date of first full or partial inhaled dose of IMP + 1.

The date of last full or partial inhaled dose of IMP is as defined in Section **Error! Reference source not found.**

The extent of exposure will also be calculated in weeks using the following formula:

- Extent of exposure (weeks) = Extent of exposure (days) / 7.

Dose of IMP either at the investigational site or at home will be considered.

Treatment exposure will be summarised overall and by treatment group for the Safety and mITT Populations using descriptive statistics for continuous variables.

4.5.4 Adherence

Adherence will be calculated overall.

The evaluation of adherence will be based on the following formula:

- Adherence (%) = (# Total Inhaled Doses / # Scheduled Doses)*100.

The total number of inhaled doses of IMP will be computed as described in Section 4.5.1. In cases where, due to the Covid-19 pandemic, the final dose registered on the **CCI** device is the dose given at the in-clinic part of a split Visit 7 for the purposes of bronchospasm testing, any dose on the **CCI** that is later than the date of last IMP administration as entered on the End of Study eCRF form will not be counted as an inhaled dose for the calculation of IMP adherence.

The scheduled doses will be computed as 2 times the total number of days from Visit 2 to the end of period date, i.e. (End of period date – date of Visit 2) + 1.

For the overall adherence, the end of period date will be the date of the last inhaled dose of IMP, based on the latest of the last dose recorded in the **CCI** download (with the exceptions noted above relating to split Visit 7's) or the date of the last dose of IMP recorded in the End of Study form in the eCRF.

Adherence will be summarised by treatment group and overall for the mITT Population, presenting descriptive statistics for continuous variables and absolute and relative percentages of subjects considered to be adherent, i.e. with a least 80% of adherence.

CONFIDENTIAL

Sponsor:	Zambon S.p.A.	Protocol Number:	Z7224L02
----------	---------------	------------------	----------

An additional summary displaying the number and percentage of subjects in the following categories will also be presented by treatment group:

- <60%;
- 60 to <70%;
- 70 to <80%;
- 80 to <90%;
- ≥90%.

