If subjects need to be CCI [REDACTED] for intravenous antibiotics, they should be visited by the research staff for an assessment within 72 hours of admission (where possible). If the subject is CCI [REDACTED] that is not the investigational site, the assessments should be carried out (where possible) by the CCI [REDACTED] under the direction of the investigational site. These assessments will include those collected during exacerbation visits/contacts and will include details regarding any interruption of IMP administration. In these circumstances, every effort should be made to complete all assessments although it is recognised that this might not be possible.

Telephone calls will be made to patients on a weekly basis during a NCFB pulmonary exacerbation until resolution to assess the progression of symptoms and to determine whether systemic antibiotic treatment is ongoing. A telephone script will be provided to sites and responses to standardised questions will be collected in relevant eCRFs.

Resolution of a NCFB pulmonary exacerbation is defined as the date of completion of the required course of systemic antibiotic treatment or the Investigator's judgement that the NCFB pulmonary exacerbation has resolved, whichever is later. This is also the end date of the corresponding AE. Exacerbations occurring less than 14 days after the end of a course of systemic antibiotics for a NCFB pulmonary exacerbation will be considered as a single event (see [Section 10.1.5](#)).

IMP administration may be temporarily interrupted during the time of systemic antibiotic treatment due to a pulmonary exacerbation based on the Investigator's judgement; thereafter, the study treatment should restart as soon as possible. Stop date and re-start date will be recorded in the relevant eCRF. The occurrence of a pulmonary exacerbation does not mandate the discontinuation of the subject from the trial and/or study treatment, unless it occurs between Visit 1 and Visit 2 and/or the Investigator believes discontinuation is in the subject's best interest.

The following assessments will be performed at an Exacerbation Visit or Phone contact, and all details of the pulmonary exacerbation have to be recorded:

- start date and duration of all symptoms since the start;
- all symptoms present which support the NCFB pulmonary exacerbation diagnosis;
- all concomitant medications, especially systemic antibiotics;
- physical examinations and vital signs (if attending the clinic);

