3.5.4 Per-Protocol Population

The Per-Protocol Population (PP) will include all mITT subjects who were considered compliant with study drug administration (i.e. had an adherence of at least 80%) and who had no major protocol deviations that were considered as potentially impacting the efficacy results.

Major protocol deviations might include, but are not limited to, subjects taking a not-permitted concomitant medication, the IMP not being administered during the trial as defined in the protocol, subjects receiving a treatment different than the one assigned by randomisation. Categories of protocol deviations and additional details are reported in Section 4.10. The exact definition of major protocol deviations impacting the efficacy results will be discussed by the study team during the blind review of the data and described in the Blind Data Review and Analysis Sets Report.

Results of the primary and relevant secondary efficacy endpoints analyses conducted for the

CONFIDENTIAL

Sponsor:	Zambon S.p.A.	Protocol Number:	Z7224L02
----------	---------------	------------------	----------

PP will be considered as supportive.

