4.1.5 Subgroup Analyses

The mean annual NCFB pulmonary exacerbation rate will also be estimated in the following subgroups:

1. Number of NCFB pulmonary exacerbations requiring oral or intravenous antibiotics in the 12 months prior to study entry.

The number of NCFB pulmonary exacerbations requiring oral antibiotics in the last 12 months and the number of NCFB pulmonary exacerbations requiring intravenous antibiotics in the last 12 months prior to study entry, as collected in the eCRF Screening folder on the Non-CF Bronchiectasis History form, will be summed.

Subgroup results will be presented for subjects with 1, 2 and >2 NCFB pulmonary exacerbations in the last 12 months.

Subjects with no data regarding the number of NCFB pulmonary exacerbations requiring oral and/or intravenous antibiotics in the last 12 months prior to study entry will be excluded from the analysis.

CONFIDENTIAL

Sponsor:	Zambon S.p.A.	Protocol Number:	Z7224L02
----------	---------------	------------------	----------

2. Previous usage of colistimethate sodium/colistin (as collected on the Non-CF Bronchiectasis History eCRF form).

Based on data collected on the Non-CF Bronchiectasis History eCRF form regarding previous usage of Colistimethate Sodium/colistin, the subjects will be classified into one of the following groups:

- i. Without any previous usage of colistimethate sodium/colistin;
- ii. With previous usage of colistimethate sodium/colistin.

Subjects with missing data regarding previous usage of colistimethate sodium/colistin will be excluded from the analysis.

3. **CCI** will be presented classifying subjects by status of previous usage of colistimethate sodium/colistin as collected on the Non-CF Bronchiectasis History eCRF form. Subjects with missing data regarding previous usage of colistimethate sodium/colistin will be included in the analysis in a separate ‘unknown’ subgroup.

Additional subgroup analyses for the mean annual NCFB pulmonary exacerbation rate endpoint will include:

4. Age at Visit 1 (<65, >=65)
5. Sex (Female, Male)
6. Country; for this, and all analyses using country, the small countries with few subjects will be grouped into a single ‘Other’ country category. Based upon blinded data, the smaller countries to be grouped are: Germany (N=3), Greece (N=3), Israel (N=4), Italy (N=1), New Zealand (N=6) and Portugal (N=2)
7. Adherence (compliance to IMP <80%, >=80%, Unknown).

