4.5.5 IMP interruptions

The number and percentage of subjects with at least one IMP interruption, the number and percentage of subjects with at least one IMP interruption due to NCFB pulmonary exacerbation and the number of NCFB pulmonary exacerbations which lead to an IMP interruption will be presented.

Moreover, the number of days of IMP interruption overall and due to NCFB pulmonary exacerbations will be summarised using descriptive statistics for continuous variables.

Results will be presented overall and by treatment group for the Safety and mITT Populations.

Notes:

- NCFB pulmonary exacerbations will be linked to the corresponding AE using the AE number collected in the eCRF form “Pulmonary Exacerbation”, i.e. “Please specify corresponding Adverse Event number for this Pulmonary Exacerbation”.
- IMP interruption (days) will be calculated considering stop date and re-start date of IMP as collected in the eCRF “Adverse Event” form using the following formula:

$$\text{IMP interruption (days)} = \text{Re-Start date of IMP} - \text{date of Stop of IMP} + 1.$$
- If any dose with a dose different than “Null” is recorded in the **CCI** logging system during this period, then the **CCI** data will be considered to compute IMP interruption: stop date will be the last IMP dose date before the start of the AE, re-start date will be the first IMP dose date after the start date of the AE.

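### Adherence counts permitted exacerbation-related dosing gaps as missed doses, so the per-protocol set and the ≥80% adherence subgroup are partly selected on the primary outcome

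*SAP*

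**What the plan says.** SAP 4.5.4 defines "Adherence (%) = (# Total Inhaled Doses / # Scheduled Doses)*100". For the denominator, "The scheduled doses will be computed as 2 times the total number of days from Visit 2" to the end of the period, and "the end of period date will be the date of the last inhaled dose of IMP", taken as the later of the device log and the End of Study form, with an exception for split final visits. No interruption days are removed.

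Protocol 9.7 states that "IMP administration may be temporarily interrupted during the time of systemic antibiotic treatment due to a pulmonary exacerbation", at the investigator's judgement and with a prompt restart. SAP 4.5.5 derives the length of these gaps, but only to describe them: "the number of days of IMP interruption overall and due to NCFB pulmonary exacerbations will be summarised".

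The score, cut at 80%, does two jobs:

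- It decides PP membership. SAP 3.5.4 requires that a subject "had an adherence of at least 80" per cent, and Protocol 19.4.1 sets the same threshold.
- It forms subgroup 7 in SAP 4.1.5: "Adherence (compliance to IMP <80%, >=80%, Unknown". SAP 4.7.4.3 fits its interaction with treatment and shows it, with the interaction p-value, in one forest plot beside age, sex and country. SAP 4.7.6.1 also applies it to a secondary time-to-event endpoint.

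The primary analysis is on the mITT population, and PP results are supportive (SAP 4.7).

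**The concern.** The primary endpoint counts exacerbations treated with systemic antibiotics. Those same events are the occasion on which the protocol allows dosing to pause, and every paused day then scores as two missed doses. A subject who follows the protocol exactly can drop below 80% because of the outcome being measured. Entry to the PP set and to the ≥80% stratum therefore falls as the exacerbation count rises. Rates within each stratum, and comparisons between strata, partly reflect how subjects were sorted.

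The end of the clock is a separate matter that acts the other way. A subject who takes every dose for a few weeks and then stops for good scores about 100% and stays in the PP set, whatever the reason for stopping.

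**Working it through.** **1. Anchor rates.** The adherence rule has no computed figure to reproduce. The rates come from the Protocol summary (Sample Size): placebo 1.09 per year, a 35% reduction (so 1.09 × 0.65 = 0.7085), and 170 completers per group for 90% power at two-sided 0.05. The variances are redacted, so the dispersion k is an assumption. With var(log ratio) = (1/1.09 + 1/0.7085 + 2k)/170:

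- k = 0 gives 95.7% power.
- k = 0.30 gives (0.917 + 1.411 + 0.600)/170 = 0.01723, a standard error of 0.131 and power of 90.7%. For a 30% effect it gives 79.0%, against 80% stated.
- k = 0.337 gives 90.0% for the 35% effect and is used below.

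**2. The formula itself.** If a subject takes a fraction u of doses on non-interrupted days, has g interrupted days, and the clock runs T days, then adherence = u × (T − g)/T. The gap unit of 14 days is an assumption based on the antibiotic course length in Protocol 10.1.5.

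- 0.90 × (365 − 42)/365 = 79.6%
- 0.85 × (365 − 28)/365 = 78.5%
- 0.95 × (365 − 60)/365 = 79.4%
- 0.90 × (120 − 14)/120 = 79.5%

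Short follow-up is realistic. SAP 3.9 says recruitment stopped in November 2021, and SAP 4.7.4.2 sets closure at 28 February 2022. A subject randomised on 1 November would have 30 + 31 + 31 + 28 = 120 days.

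Interrupted days needed to reach the 80% line over 365 days, from 365 × (1 − 0.80/u): 73.0 for u = 1, 57.6 for 0.95, 40.6 for 0.90 and 21.5 for 0.85.

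**3. Effect on the sets.** Simulation with 400,000 subjects per arm and 365 days. Assumptions not in the documents: u follows Beta(13.5, 1.5) (mean 90%), independent of exacerbations; the share of exacerbations that interrupt dosing and the gap length are as tabulated, and equal by arm. True placebo rate 1.09, true ratio 0.65.

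| Share interrupting | Gap (days) | Placebo rate, ≥80% | Placebo rate, <80% | Ratio, ≥80% | Ratio, <80% |
|---|---|---|---|---|---|
| 25% | 14 | 1.06 | 1.32 | 0.655 | 0.642 |
| 25% | 28 | 0.98 | 1.62 | 0.666 | 0.642 |
| 50% | 14 | 1.01 | 1.56 | 0.660 | 0.626 |
| 50% | 28 | 0.85 | 1.91 | 0.681 | 0.677 |
| 100% | 14 | 0.85 | 1.99 | 0.699 | 0.636 |
| 100% | 28 | 0.54 | 2.08 | 0.760 | 0.742 |

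Placebo subjects with 0, 1, 2, 3 and 4 exacerbations enter the ≥80% set at 89, 86, 82, 77 and 70% if half of exacerbations cause a 14-day gap, and at 90, 83, 73, 57 and 33% if all do.

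With no true effect, the ratio in the ≥80% set stays at 1.00 in every row. With gap days taken out of the denominator, about 89.5% of each arm reaches 80% and the ratio there returns to about 0.65.

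**4. End of the clock.** A subject who takes every dose and stops on day 30 scores 60/60 = 100%. Over an expected 365 days the score is 60/730 = 8.2%. Stopping on day 90 gives 24.7% and on day 180 gives 49.3%.

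**5. Is the SAP 4.5.5 gap usable as it stands?** It is restart date − stop date + 1. With a last dose on day 100 and the next on day 115, there are 14 dose-free days (101 to 114), but the formula gives 115 − 100 + 1 = 16. When both dates are dosing days, as under the device-log rule, subtracting it removes two days too many.

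**The case against.** Nothing confirmatory depends on this score. A reader might infer that the primary result is biased, but the documents do not support that: the primary analysis uses all mITT subjects regardless of adherence.

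Interruption is optional, and Protocol 9.7 also allows antibiotics to be added while IMP continues. At the planned rates, with k of 0.30 to 0.34, only about 12% of placebo and 5% of active subjects have three or more exacerbations. To produce 42 interrupted days from 14-day gaps, three events must each interrupt dosing. With few interruptions the ratio hardly moves. That stands, and it limits the size of the point.

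A reader might also infer that the treatment ratio can be distorted in either direction, or that a false benefit could arise. With equal interruption patterns by arm, the ratio in the ≥80% set moves only towards 1, and it does not move at all under the null. Movement away from 1 in that set would need patterns that differ by arm, and the documents give no sign of this in a double-blind trial.

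Nor do both rules select low-event subjects. The last-dose clock retains early stoppers, including any who stopped because of an exacerbation.

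It is also arguable that a subject off drug for many weeks does not belong in a set meant for compliant use, so the present formula is a choice rather than an error. And an adherence split has a precedent in the Phase 2 results (Protocol Section 4). That precedent also shows why such a split is not a randomised comparison. In its placebo arm, 39 of 54 adherent patients had an exacerbation, against 42 − 39 = 3 of the other 71 − 54 = 17. Adherence was thus related to outcome without active drug, there in the direction opposite to the interruption mechanism.

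**Conclusion.** The point holds with limited reach. Because permitted gaps count as missed doses, membership of the PP set and of subgroup 7 depends partly on the exacerbation count. Blinded review of PP exclusions does not change that, since the formula carries the dependence.

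The rates within strata are the more vulnerable output. The simulated placebo rate in the ≥80% set falls from 1.09 to between 1.06 and 0.54, and in the <80% set it rises to between 1.32 and 2.08. The ratio in the ≥80% set moves from 0.65 to about 0.66 under 14-day gaps after a quarter to a half of exacerbations, and to 0.70 or 0.76 if every exacerbation causes a 14-day or 28-day gap. The ratio in the <80% set can sit lower, for example 0.626 against 0.660, so a difference between strata can appear where the true effect is the same in both.

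All of these sizes rest on assumed interruption frequency and length, assumed underlying adherence and dispersion, and equal patterns by arm. The dependence itself needs only the formula and the occurrence of exacerbation-related gaps after which dosing resumes. The early-stopper issue is real but separate. This is a cheap improvement to supportive and exploratory output.

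**What to change.** - **Denominator.** For the PP rule and the adherence split, exclude from scheduled doses the dose-free days of recorded exacerbation-related interruptions, counted as days strictly between the last dose before and the first dose after the gap. Do not subtract the SAP 4.5.5 figure unmodified. Keep the present formula as a sensitivity version.
- **Adherence split.** Report it as a post-randomisation, descriptive result, outside the forest plot and without an interaction p-value, for both the primary rate and the time-to-event endpoint.
- **Early stoppers, if they are to be addressed.** Run the clock over the subject-specific expected period t_j already defined in SAP 4.7.4.2. The treatment discontinuation date would not help: SAP 4.1.7 sets it at the End of Study Visit, so a subject who stops in week 3 and is seen promptly still scores near 100%. Using t_j also avoids marking subjects cut short by the closure as non-adherent against 365 days, although it runs slightly long for anyone whose closing visit was called before 28 February 2022.

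The cost is one derivation from data already collected, some SAP wording and one moved display. The downside is that some subjects with long permitted gaps off drug stay in the PP set, which is why the present formula should remain as a sensitivity version. If the blind has already been broken, SAP Section 1 requires the change to be labelled post hoc.
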